1.A. Impact of stroke on individuals and populations. Stroke is the 4th leading cause of death and leading cause of serious long-term disability in the U.S. Every year, more than 795,000 people in the U.S. have a stroke with one new stroke occurring every 40 seconds¹. It is projected that by 2030 4% of the American population would have had a stroke. Stroke incidence is particularly high among younger African-Americans, lower socioeconomic groups, and in the Southeast U.S. including east Texas and Tennessee, two of the seven centers in this proposal². More than 70% of stroke patients are unable to return to their pre-stroke life style, activities of daily living and employment. AIS results from a blood clot blocking an artery to the brain and accounts for 87% of all strokes. Intravenously administered tPA is a highly effective treatment for AIS that can be carried out in the prehospital or Emergency Department (ED) setting³. Clinical trials consistently confirm the relationship of treatment success with decreased time from last-seen-normal (LSN) to initiation of treatment⁴⁻⁸. However, despite two decades of efforts to streamline Healthcare systems, most patients are treated beyond 2 hours, since treatment has been ED-based and the median door to needle times in stroke center EDs in the U.S. approximates 60 minutes^{9,10}. Such delay contributes to the overall low national tPA treatment rate--about 5% of all AIS, with only 0.0005% or 1 out of 2,000 stroke patients treated within the first hour after onset. Recently, substantially faster treatment with tPA became a reality after German researchers placed a Computed Tomography (CT) scan and physician on an ambulance with treatment safely "taken to the patient" 11. This MSU increased treatment rates from 21% to 33% with 25 min shorter time to treatment¹². Thirty-one percent of MSU tPA patients were treated within 60 minutes of onset compared to 4.9% with Standard Management (SM), and these patients had an OR of 1.93 (95% CI 1.09-3.41) of discharge to home compared to later treatment¹³. In addition, recent transformative trials 14-17 have shown substantial benefit from intra-arterial mechanical thrombectomy (IAT) for patients with the most severe strokes, and also demonstrate that patients who achieve recanalization quickly benefit most. MSUs might speed IAT by allowing prehospital identification of appropriate patients and shortening in-house delays incurred by acquiring imaging/labs, treating with tPA, and assembly of the IAT team, perhaps allowing bypass of ED evaluation altogether. Therefore, the MSU strategy may substantially improve outcomes for patients with AIS, and dramatically alter the Healthcare system for all acute stroke patients.

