The MSU is not dispatched, but the MSU RN or VN is 5.C.4. Standard management: dispatched by car to the scene or meets the patient and EMS squad at the destination ED. The destination CSC is determined by EMS (these are the same complement of hospitals served by the MSU) and the hospital stroke team is pre-notified by EMS. Once on scene or at the ED, the patient's history, time last seen normal, vital signs, finger stick glucose, and physical examination are obtained from the EMS paramedics by the MSU VN or RN who then carry out their own NIHSS without delaying the EMS evaluation, transport or ED intake process, If the patient meets all inclusion criteria except lab and CT (which have not yet been done), the patient is then enrolled into the study for purposes of answering the Specific Aims, and assigned to the SM arm. If the patient does not have signs and symptoms of a stroke, is clearly outside the 4.5 hour time window, has other definite tPA exclusions, or is clinically unstable (such as requiring pressor or ventilator support), they are not enrolled and are managed per EMS and ED routine. These patients are considered "screen failures" and a one page CRF completed including diagnosis and reason for exclusion. Following the decision to enroll the patient, the MSU VN or RN then decide if the patient meets criteria for tPA. If the patient meets all inclusion and exclusion criteria for thrombolysis according to published guidelines during the pre-hospital evaluation by EMS and the MSU team, and if the baseline labs and CT scan obtained once the patient reaches the ED do not exclude the patient, then the patient is considered a "SM tPA-eligible patient", whether or not they eventually receive tPA in the ED (for instance, the 4.5 hour time window might be exceeded, or the patient's deficit might have resolved, by the time the patient is fully evaluated in the ED).

The hospital based stroke team manages the patient as per stroke center routine and the same standard of care analyses carried out as with the MSU treatment. IV tPA is given as per the hospital based stroke team. If the patient does receive tPA in the ED, the "therapy decision time", and "tPA needle time" are recorded. For all SM enrolled patients, whether or not they actually receive tPA, the RN or VN obtain consent, and visit the patient on days 0-3 at the hospital and day 90 in clinic or at home, and record study related data on the CRF.

TM is not carried out on SM weeks.

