2.2.3. Safety Outcomes

- The incidence of symptomatic intracranial hemorrhage (sICH) in enrolled tPA treated patients on MSU weeks compared to SM weeks (Symptomatic intracranial hemorrhage defined as any intracranial blood accumulation associated with a clinical deterioration of ≥ 4 points of the NIHSS for which the hemorrhage has been identified as the dominating cause of the neurologic deterioration) N.B. Patients will include all patients treated with tPA, whether or not they meet all inclusion and exclusion criteria.
- Mortality. N.B. All enrolled patients signing informed consent will be included in this endpoint and followed until 1 year.
- The incidence of stroke mimics and transient ischemic attacks (TIAs) in tPA-treated patients, and also in tPA-eligible patients, on MSU weeks compared to SM weeks. N.B. SM patients deemed eligible for tPA on their pre-hospital assessment who then completely recover by the time of arrival in the ED will equal the excess incidence of TIAs treated on the MSU pathway.

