5.1.4. Analyses of Ancillary Clinical Outcomes

We will also compare mRS at 90d (uw-mRS, Δ uw-mRS from baseline, ordinal (shift) analysis, and proportion achieving 0,1) in tPA treated patients treated within 60 minutes of LSN to patients treated 61-270 minutes, regardless of whether they were on MSU weeks vs. SM weeks. Patients on MSU weeks vs SM weeks will also be compared for differences in (a) the time from LSN to tPA treatment, (b) time from LSN, alarm time, and ED arrival to start of IAT, and for safety outcomes (i) mortality, (ii) symptomatic intracerebral hemorrhage, and (iii) incidence of tPA treated stroke mimics and transient ischemic attacks.

A logistic regression model will be used to compare 90 day mRS 0,1 vs 2-6 of patients treated with tPA within 60 minutes of symptom onset to similar patients treated 61-270 minutes after onset, adjusting for any imbalances in stroke severity (baseline NIHSS, age, premorbid mRS, and previous stroke/TIA incidence) between the groups at the time of treatment⁸. If baseline characteristics are significantly different between the two non-randomized groups, we will use propensity score analysis to limit potential bias. Also, we expect a higher incidence of spontaneous recovery (TIA) and stroke mimics may occur with earlier observation in the 0-60 minute group compared to those seen 61-270 minutes. The “natural history” of the incidence of spontaneous recovery and stroke mimics will be estimated from patients enrolled into the SM group, and will be considered in analyzing the comparison between patients treated with tPA within 0-60 min vs 61-270 min. Time to treatment and to endovascular procedures will be analyzed using Cox proportional hazards models, similarly to survival. Categorical outcomes will be analyzed using Fisher’s exact test.

Unless there is sufficient power (predetermined before the analysis is begun) the approach to ancillary analysis will generally be the calculation of confidence limits on intervention group differences rather than formal tests of significance as the trial may not have high power to detect difference in all of these outcomes. However, these comparisons will add to the knowledge of the benefits and risks of the intervention.

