6.4. Safety Analyses

Rates of symptomatic hemorrhage will be compared using a Fisher's exact test ($\alpha=0.05$). This will be conducted on all enrolled tPA-treated patients, excluding any that had an ICH on their baseline CT scan.

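### Symptomatic haemorrhage is compared only per tPA-treated patient, a group the MSU is expected to enlarge and change; add an estimate per tPA-eligible and per enrolled patient

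*SAP*

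**What the plan says.** SAP 2.2.3 defines the bleeding endpoint as "The incidence of symptomatic intracranial hemorrhage (sICH) in enrolled tPA treated patients on MSU weeks compared to SM weeks" and adds: "Patients will include all patients treated with tPA, whether or not they meet all inclusion and exclusion criteria". The Protocol synopsis (safety endpoints) and Protocol 6.B.1 define it in the same way. SAP 6.4, on interim safety monitoring, says "Rates of symptomatic hemorrhage will be compared using a Fisher's exact test" and sets the population: "This will be conducted on all enrolled tPA-treated patients, excluding any that had an ICH on their baseline CT scan". SAP 5.1.4 lists sICH among the safety comparisons without a denominator.

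No section plans sICH per tPA-eligible or per enrolled patient. The other main outcomes rest on groups that do not depend on treatment:

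- The primary outcome uses all adjudicated tPA-eligible patients, treated or not (SAP 2.2.1, 3.1).
- Mortality covers all consented enrolled patients to one year (SAP 2.2.3).
- Mimic and TIA incidence is given per treated and also per tPA-eligible patient (SAP 2.2.3).

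The documents also expect the strategy to change who is treated:

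- Protocol 1.A reports of an earlier unit: "This MSU increased treatment rates from 21% to 33% with 25 min shorter time to treatment".
- Protocol 3.C.2 gives a higher probability of tPA administration as an aim.
- Protocol 5.C.4 explains why eligible SM patients may go untreated: "the 4.5 hour time window might be exceeded, or the patient's deficit might have resolved".
- SAP 2.2.3 says that SM patients who recover before ED arrival "will equal the excess incidence of TIAs treated on the MSU pathway".

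**The concern.** Being treated with tPA is a consequence of the strategy. If the MSU treats more of the same kind of patient, the sICH rate per treated patient need not move, although more patients bleed. If the extra patients are at lower risk, such as TIAs or mimics, the MSU rate per treated patient can fall while the number of bleeds rises. SAP 5.1.5 itself warns that analyses of subgroups formed after randomisation are open to many biases, yet the only planned sICH comparison is of that kind.

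What is at stake is the benefit-risk statement for the strategy. The primary outcome credits the MSU for treating eligible patients whom SM would have missed. The planned sICH figure does not show what that extra treatment costs in bleeds, on the same base.

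**Working it through.** The documents give no sICH rate, margin or expected event count. The only planned figure to reproduce is the size of the primary cohort, which sets the scale.

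**1. Cohort size.** Inputs from SAP 4.1: difference 0.07, SD 0.385, MSU:SM ratio 1.5, 5% loss. The 80% power and 0.05 type I error are stated for the 0.09 design and assumed to carry over (two-sided).

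- SM: (1 + 1/1.5) × (1.96 + 0.8416)² × (0.385/0.07)² = 1.667 × 7.849 × 30.25 ≈ 396.
- MSU: 1.5 × 396 = 594. Total 990.
- With 5% loss: 990/0.95 gives 1043, and 990 × 1.05 gives 1040. The stated 1038 is reproduced to within 1%.
- A 3:2 split of 1038 is 623 MSU and 415 SM.

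**2. Equal risk per treated patient.** sICH per base patient = proportion treated × sICH risk per treated patient, where the base is the group before the treatment decision. If the risk per treated patient is equal, the planned ratio is 1.00, and the base-patient ratio equals the ratio of treated proportions. The sICH risks of 2%, 4% and 6% are assumptions.

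| Treated, MSU vs SM | Source | Base-patient ratio | sICH per 1000 at 2% | at 4% | at 6% |
|---|---|---|---|---|---|
| 97% vs 90% of eligible | assumed | 1.08 | 19.4 vs 18.0 | 38.8 vs 36.0 | 58.2 vs 54.0 |
| 97% vs 80% of eligible | assumed | 1.21 | 19.4 vs 16.0 | 38.8 vs 32.0 | 58.2 vs 48.0 |
| 33% vs 21% | earlier study, Protocol 1.A | 1.57 | 6.6 vs 4.2 | 13.2 vs 8.4 | 19.8 vs 12.6 |
| 50% vs 50% of enrolled | Protocol 7.I.2, SAP 5.2.2 | 1.00 | 10 vs 10 | 20 vs 20 | 30 vs 30 |

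The excess per 1000 at 2%, 4% and 6% is 1.4, 2.8 and 4.2 in the first row; 3.4, 6.8 and 10.2 in the second; 2.4, 4.8 and 7.2 in the third; and zero in the last.

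**3. Dilution.** Suppose the extra patients treated by the MSU bleed at 1% and all others at 4% (assumed).

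- 33% vs 21%: MSU bleeds per base patient = 0.21 × 0.04 + 0.12 × 0.01 = 0.0096; SM = 0.21 × 0.04 = 0.0084. Per treated patient, MSU is 0.0096/0.33 = 2.9% and SM 4.0%. Per 1000 base patients it is 9.6 vs 8.4.
- 97% vs 80%: 0.80 × 0.04 + 0.17 × 0.01 = 0.0337 vs 0.0320. Per treated patient, 0.0337/0.97 = 3.5% vs 4.0%. Per 1000, 33.7 vs 32.0.

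In both cases the planned rate favours the MSU while the MSU arm has more bleeds. If the extra patients never bleed, the number per base patient is equal and the planned rate still favours the MSU.

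**4. Precision.** At 97% vs 80% treated and 4% risk, the per-eligible difference is 3.88% − 3.20% = 0.68 percentage points. Its standard error is √(0.0388 × 0.9612/623 + 0.0320 × 0.9680/415) = 0.0116, so the 95% CI is about ±2.3 points. By exact enumeration, a two-sided Fisher test per eligible patient would be significant with probability 4.7%, 7.3% and 9.5% at risks of 2%, 4% and 6%. The per-treated test gives 3.6%, 4.2% and 4.2%. An added test would settle little; an added estimate is what is useful.

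**The case against.** A reader might infer three stronger things, and the documents support none of them.

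- *That bleeds in the extra patients are not counted.* They are: SAP 2.2.3 takes every treated patient, eligible or not. The fault lies only in the denominator.
- *That equal per-treated rates would be reported as no harm.* No section says so. SAP 5.1.4 generally prefers confidence limits to tests for ancillary outcomes, and SAP 3.3 promises caution with secondary analyses.
- *That sICH per patient would be 57% higher in this trial.* The 33% and 21% come from another study, quoted in Protocol 1.A without a denominator. For this trial, Protocol 7.I.2 and SAP 5.2.2 give one planning figure of about 50% of enrolled patients for both groups. If the proportions are in fact equal, the excess is zero.

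The remaining case for the plan is fair. The per-treated rate answers a legitimate question. SAP 2.2.2 also plans functional outcomes in all treated patients, so benefit and harm share that denominator in one analysis. Fatal bleeds enter all-enrolled mortality, and disabling or fatal bleeds in eligible patients enter the primary outcome. The per-eligible burden can be approximated by multiplying the percentage of eligible patients treated by the per-treated rate. SAP 5.1.4's statement that "we expect a higher incidence of spontaneous recovery (TIA) and stroke mimics may occur with earlier observation in the 0-60 minute group" contrasts treatment times, not arms.

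These points limit the size of the problem but do not remove it. Mortality and the utility-weighted mRS do not identify sICH. The approximation is inexact, because treated patients adjudicated ineligible are in the sICH set but outside the primary cohort (Protocol 5.D). The post hoc all-enrolled analyses in SAP 5.1.2 name discharge mRS and 24-hour NIHSS, not sICH. The expectation that the MSU treats more TIAs rests on SAP 2.2.3, which does compare the arms.

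**Conclusion.** The plan has no comparison of sICH by assigned strategy in a population that the strategy does not itself select. With equal risk per treated patient, the planned ratio of 1.00 corresponds to 1.08 to 1.21 per eligible patient under the assumed treated proportions, to 1.57 at the earlier study's proportions, and to 1.00 if the proportions are equal. In absolute terms, the two assumed eligible-patient scenarios give 1.4 to 10.2 extra bleeds per 1000 at sICH risks of 2% to 6%. If the extra patients are at lower risk, the two measures can point in opposite directions. The sICH risks, the proportions of eligible patients treated and the 1% risk in extra patients are assumptions; the documents give none of them. The actual difference could be nil or favour either arm. This is a gap in reporting, cheap to close, and not evidence that the MSU causes more bleeding.

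A related inconsistency needs settling: SAP 2.2.3 counts all treated patients, while SAP 6.4 removes those with haemorrhage on the baseline CT.

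**What to change.** In SAP 2.2.3:

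1. Keep the sICH rate in all tPA-treated patients.
2. Add, as supplementary estimates with the same sICH definition, counts by group, risk difference and 95% CI in (a) all adjudicated tPA-eligible patients and (b) all enrolled patients without haemorrhage on the first CT. The restriction in (b) keeps a presenting haemorrhage that worsens from being counted as sICH.
3. Report the benefit-risk summary with both the per-treated and the per-eligible figure. The per-eligible figure alone would lose bleeds in treated patients adjudicated ineligible.
4. Reconcile SAP 2.2.3 and 6.4 on baseline haemorrhage, or state that the interim and final populations differ on purpose.

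If outcome data have been seen, the additions should be labelled post hoc, as SAP 3.1 does for the cohorts added after peer review.

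The cost is modest. Protocol 8.F records brain bleeding from enrolment to discharge without limiting it to treated patients. Protocol Figure 1 has NIHSS at baseline and 24 hours, and imaging is required on neurological deterioration. Someone must still apply the sICH definition (NIHSS worsening of at least 4 points, with haemorrhage as the dominant cause) to bleeds in untreated patients, because the recorded event carries neither criterion and follow-up imaging is otherwise optional. The estimates will be imprecise, and the harm figure may look slightly less favourable to the MSU. No clinical procedure changes.

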- **6.B.1.**The incidence of symptomatic intracranial hemorrhage (sICH) in enrolled tPA treated patients on MSU weeks compared to SM weeks (Symptomatic intracranial hemorrhage defined as any intracranial blood accumulation associated with a clinical deterioration of \geq 4 points of the NIHSS for which the hemorrhage has been identified as the dominating cause of the neurologic deterioration) **N.B.** Patients will include all patients treated with tPA, whether or not they meet all inclusion and exclusion criteria.
- **6.B.2.** Mortality. **N.B.** All enrolled patients signing informed consent will be included in this endpoint and followed until 1 year.
- **6.B.3.** The incidence of stroke mimics and transient ischemic attacks (TIAs) in tPA treated patients on MSU weeks compared to SM weeks. **N.B.** SM patients deemed eligible for tPA on their pre-hospital assessment who then completely recover by the time of arrival in the ED will equal the excess incidence of TIAs treated on the MSU pathway.

6.C. Outcomes for S.A. 2.

- **6.C.1**. The agreement between the VN on board the MSU with a VN remotely assessing a suspected stroke patient for treatment with tPA via TM in the MSU. **N.B**. Patients will include all enrolled patients on MSU weeks considered for tPA treatment.
 - **6.C.2.** Frequency and causes of incomplete or failed TM consultations.

6.D. Outcome for SA 3.

6.D.1. Determine health care utilization and QoL during the first year after the stroke on MSU vs SM weeks.

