2. DEFINITION OF TARGET POPULATION AND STUDY SAMPLES

2.1. Target Population

No. of Clinical Sites: 6

No. of subjects:

To be assessed for eligibility	(n = 4900)
To be enrolled	(n = 1845)
To be analyzed (“tPA eligible”)	(n = 1038)

Main criteria for inclusion:

1. Criteria for MSU team to enroll a patient into the study (to be determined pre-hospital on both MSU and SM weeks)

- a. Last seen normal possibly within 4hr 30 min
- b. History and physical/neurological examination consistent with acute stroke
- c. No definite tPA exclusions per guidelines, prior to CT scan or baseline labs
- d. Informed consent obtained from patient (if competent) or legal representative. Pre-hospital management and treatment, including IV tPA, will not be delayed for consent; however, consent in both MSU and SM patients must eventually be obtained for data to be retained for analysis.

2. Criteria for **tPA-eligibility** (to be determined pre-hospital on MSU weeks, and after ED assessment on SM weeks, and confirmed by blinded adjudication)

- a. Meeting tPA inclusion and exclusion criteria per guidelines after CT scan, baseline labs, and clinical re-evaluation

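### Counting SM recoveries up to ED arrival does not give the excess of TIAs treated on the MSU; the stated equality should be removed

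*SAP*

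**What the plan says.** The third safety outcome (SAP 2.2.3; protocol 6.B.3 and the synopsis) compares the incidence of stroke mimics and TIAs between MSU and SM weeks among tPA-treated patients and, in the SAP, also among tPA-eligible patients. A note then adds a rule. In the SAP, "SM patients deemed eligible for tPA on their pre-hospital assessment who then completely recover by the time of arrival in the ED will equal" MSU's excess of treated TIAs. Protocol 6.B.3 says the same of SM patients judged eligible before hospital "who then completely recover by the time of arrival in the ED will equal the excess incidence of TIAs treated on the MSU pathway".

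Other sections fix when the tPA decision is made:

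- SAP 2.1: eligibility is "to be determined pre-hospital on MSU weeks, and after ED assessment on SM weeks, and confirmed by blinded adjudication".
- Protocol 5.C.4: an SM patient counts as eligible "if the baseline labs and CT scan obtained once the patient reaches the ED do not exclude the patient". Among the reasons why such a patient may still go untreated, it names that "the patient's deficit might have resolved, by the time the patient is fully evaluated in the ED".
- Protocol 5.C.3: on the MSU, the decision follows on-board labs, CT and a repeat NIHSS.
- Protocol 5.C.4: on SM weeks the team member is "dispatched by car to the scene or meets the patient and EMS squad at the destination ED", so the first study assessment can take place at the hospital.

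Protocol 7.C and SAP 5.1.4 also estimate the natural history of spontaneous recovery from the SM group, to help interpret treatment at 0–60 versus 61–270 minutes.

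**The concern.** The extra TIAs treated on the MSU are patients who still have a deficit when the MSU team decides, but who on the SM pathway would have recovered before the ED team decided. The relevant interval runs from decision to decision. The note counts from first assessment to ED arrival, so it starts and stops too early.

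A patient who recovers half an hour after reaching the ED, before the tPA decision, is just the patient whom an MSU could have treated, yet is not counted. A patient who recovers ten minutes after first assessment, before MSU labs and CT are complete, would probably not have been treated on the MSU, yet is counted. An SM patient first met at the ED has almost no counted interval.

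The note also sets a number of SM patients equal to an MSU incidence. At stake is the trial's stated figure for how many thrombolyses on the MSU were given for deficits that would have resolved unaided.

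**Working it through.** The plan gives no numerical value for this outcome, so there is no figure to reproduce.

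**Interval identity.** Let t0 be first assessment, tM the MSU decision, tA ED arrival and tS the SM decision, with the same t0 on both pathways. Let R(a,b) be the proportion recovering spontaneously between a and b.

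- Excess sought: R(tM,tS)
- Counted by the note: R(t0,tA)
- Sought minus counted: R(tA,tS) − R(t0,tM)

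The two errors pull in opposite directions. The equality holds only if they happen to cancel.

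**Inputs**

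- D = tS − tA, about 60 min. Protocol 1.A says "the median door to needle times in stroke center EDs in the U.S. approximates 60 minutes". This is a national figure, and to needle rather than to decision, so it is a proxy.
- s = tM − t0, at most about 28 min on average. Protocol 4.C gives a mean on-scene time of 28 min (range 12–53) in the run-in, and by protocol 5.C.3 transport starts only after the decision.
- X = tA − t0, 20–30 min. This is an assumption; the documents give no value.

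**Constant low recovery rate.** Captured share ≈ X / (X + D − s):

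- X = 20: 20 / (20 + 60 − 28) = 20/52 = 38%
- X = 30: 30 / (30 + 60 − 28) = 30/62 = 48%
- X = 0 (first met at the ED): 0/32 = 0%

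At a constant rate the rule understates when D > s and overstates when D < s.

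**Front-loaded recovery.** I used Weibull recovery times with 10% recovered by 270 min after last seen normal and t0 at 25 or 45 min, all assumed. Counted divided by true, for s = 28 and X = 20–30:

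| Recovery rate | D = 60 | D = 45 | D = 20 | Break-even D (min) |
|---|---|---|---|---|
| Constant | 0.39–0.49 | 0.55–0.65 | 1.38–1.68 | 28 |
| Shape 0.7 | 0.47–0.62 | 0.64–0.79 | 1.53–1.98 | 31–34 |
| Shape 0.5 | 0.52–0.71 | 0.71–0.90 | 1.64–2.21 | 33–40 |
| Shape 0.3 | 0.58–0.83 | 0.78–1.03 | 1.75–2.46 | 36–47 |

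(The exact exponential gives 0.39–0.49 where the ratio of lengths gives 0.38–0.48.) With s = 15 and D = 60 the range over all four shapes is 0.31–0.63.

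**Count against incidence.** SAP 4.1 plans for 3:2 MSU to SM, although it also calls the groups now balanced. At 3:2, equal proportions would make 10 SM patients correspond to 10 × 1.5 = 15 MSU patients. A raw count cannot stand in for the MSU figure.

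**The case against.** The strongest reply is that the note is only a gloss. The outcome itself is a direct MSU versus SM comparison of TIA and mimic incidence. SAP 5.1.4 provides Fisher's exact test and confidence limits for such outcomes, and no estimator or test calls on the note. This stands, and it limits the consequence: the measured difference between arms is unchanged. It does not rescue the equality, which remains a stated rule for a safety quantity. Nor does either planned denominator isolate the excess: SM patients who resolve stay tPA-eligible under protocol 5.C.4, but drop out of the treated group.

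Three stronger readings are tempting, and the documents do not support them.

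- A reader might put the MSU decision at first assessment and obtain 30/90 = 33% captured, an understatement of 67%. Protocol 5.C.3 rules that out, because labs, CT and a repeat NIHSS come first.
- A reader might infer that natural recovery is thereby credited to early tPA in the 0–60 minute comparison. Protocol 7.C and SAP 5.1.4 name the SM group as the source but set no ED-arrival cut-off and do not refer to the note.
- A reader might infer that the primary comparison is affected. It is not: eligible patients stay in it whether treated or not (protocol 5.D, SAP 3.2).

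The objection that the direction is unproven also stands. D rests on a national door-to-needle median, and SAP 5.1.4 itself expects more spontaneous recovery with earlier observation, which is consistent with a front-loaded curve. The number of SM patients first met at the ED is unknown.

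**Conclusion.** The equality is wrong as written. This needs no numerical assumption: the documents' own account of when each pathway decides shows that the counted interval begins and ends too early, and protocol 5.C.4 contradicts the ED-arrival cut-off.

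Understatement is probable but not proven. On the documents' nearest timings and the assumed 20–30 min to ED arrival, the rule captures less than the full excess under every recovery curve tried. It reverses if the ED decision takes less than about 28–47 min, depending on the curve. That threshold uses s at its 28 min bound; at s = 15 it falls to 15–26 min. The size should be read as a range, not as an estimate. This is a bounded fault in one safety statement, worth correcting because correction is cheap.

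**What to change.** 1. In SAP 2.2.3, protocol 6.B.3 and the synopsis, delete the clause equating SM recoveries with the MSU excess, and reconcile the text with protocol 5.C.4.
2. Estimate the spontaneous-recovery component as a proportion with 95% CI. Denominator: SM patients assessed on scene who meet pre-hospital tPA criteria. Numerator: those whose deficit resolved before the ED tPA decision, split at ED arrival.
3. Call this an approximation that leans high, since some of these patients would also have recovered before an MSU decision. At a constant rate and the inputs above it would be 80/52 = 1.54 or 90/62 = 1.45 times the excess. Where the initial and post-CT NIHSS on the MSU allow, report the proportion recovering between them; that estimates the part to subtract.
4. Beside it, report tPA-treated patients with a final diagnosis of TIA and, separately, of mimic, per enrolled patient, MSU minus SM with 95% CI. Note that a TIA label after tPA may include strokes aborted by treatment.
5. If an SM recovery rate is used for the 0–60 versus 61–270 minute comparison, use the rate up to the ED decision.

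The cost is wording plus some chart review. Protocol 5.C.4 records therapy decision time on SM weeks only when tPA is given, although SAP 2.2.2 plans that time for all enrolled patients meeting inclusion criteria. The synopsis lists NIHSS at treatment and at ED arrival, but no deficit status at the ED decision for untreated patients. The resulting figure may be less favourable to the MSU.
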